### 5.3 Strategies for Recruitment and Retention

We will use prior successful strategies in recruiting and also solicit input from our stakeholders. Strategies that will be used are as follows: Service coordinators at all 22 facilities will serve as site liaisons. The study PI/project manager will provide the service coordinators with an introductory letter/flyer containing study information to be given to tenants and to be posted in public areas of the facility. Service coordinators will first arrange an informational meeting (study dentist will give a talk on the interventions as suggested by our stakeholders), and will arrange a second recruitment meeting for study staff to present information regarding the study at scheduled group events (e.g. tenant meetings, health fairs). For planning purposes, service coordinators will have a sign-up sheet for those interested in the sessions. Study staff will schedule those who are interested and meet the inclusion criteria for one-on-one sessions at the housing facility to obtain informed consent and collect baseline survey data. Baseline dental exam and treatment appointments will then be scheduled at each facility according to a designated exam day(s) for each facility, which will occur approximately 1-2 weeks following consent and baseline data collection. Six and twelve month dental exams/treatment and one-on-one interviews for follow-up survey completion for each time point will also occur at the housing facility where participants reside

Retention strategies for participants will include:

- Participants will be given promotional items (i.e. pens, magnets) with the study logo and contact phone number at recruitment.
- Alternate contact information for family/friends that may be able to reach the participant if primary contact information becomes invalid will be obtained at recruitment.
- Annual birthday/holiday cards will be sent to participants to maintain contact.
- Newsletters will be sent twice a year with updates on the study's progress (i.e. recruitment), and a reminder to update their contact information (by phone or mail).
- Assistance from service coordinators or other facility staff will also be solicited for hard to reach/contact participants.
- *Due to COVID-19 delays, an additional 4 housing sites are being added to the study to accelerate recruitment.*

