### **5.5.2 *Handling of Subject Withdrawals or Subject Discontinuation of Study Intervention***

All reasons for dropout/withdrawal or discontinuation of the study intervention will be documented in the tracking database and reviewed by the study team and reported to the DSMB. For gathering information on discontinuation, study staff will be contacting participants at several time points. Study staff will contact participants by phone 2-3 days before all exam and treatment visits to remind participants of the appointment, 2-3 days before all one-on-one interview appointments for survey completion, and 24 hours after all dental exam and treatment visits to complete the safety questionnaire. Participants will also be seen in person for all exam and treatment appointments and one-on-one interview appointments for survey completion.

In the event of a subject telling study staff that he/she is dropping out of the study, the study staff should gather the following information as much as the participant allows.

- Record the reason for dropping out of the study.
- Record any adverse event reported by the subject.
- Complete the appropriate questionnaire nearest the drop out time point.

If it is determined by study staff that a participant should be discontinued from the study, the decision to withdraw a participant must be discussed and confirmed by the PI.

Participants that withdraw during the baseline data collection window will be replaced by recruitment of additional participant to reach enrollment goals. Participants that withdraw or that are lost to follow-up any time after the baseline data collection window will not be replaced, but data collected up to the point of withdrawal will be used for analysis.

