## 7 STUDY SCHEDULE

Prior to any of the following actions, facilities will be randomized into one of two treatment intervention arms.

Refer to Appendix A for the Schedule of Events.

Temporary COVID-19 pandemic procedures:

Recruitment/Enrollment

- Study staff will receive contact information from Service Coordinators/Housing Managers for those who are interested in the study.
- Study staff will contact interested individuals by phone or video-conference and send them paper consent forms. They will review the consent form with the individual by phone or video-conference and answer any questions they may have and ensure the individual understands the study and all study procedures.
- Individuals will then be asked to sign the consent form and mail it back to the study staff in a stamped, self-addressed envelope provided to them. Study staff will sign the form and send a copy of the signed form back to the individual, along with a paper copy of the surveys.
- Study staff will then contact the individual by phone or video-conference to complete the surveys. Individuals will be asked to follow along on the paper survey while study staff reads the questions to them over the phone or video conference. Participant responses will be entered into REDCap by study staff during the phone call or video-conference.
- Exam/treatment appointments will be scheduled once the housing sites, funding agencies, IRB and CWRU have approved study personnel returning to being on-site at the housing sites.

26 and 52-week Follow-Up Data Collection

- Study staff will contact individuals due for the 26 and 52-week follow-up survey, to arrange a time to complete the survey by phone. Study staff will mail the survey to the individual prior to the survey completion phone call.
- Study staff will then contact the individual by phone at the scheduled time to complete the surveys. Individuals will be asked to follow along on the paper survey while study staff reads the questions to them over the phone. Participant responses will be entered into REDCap by study staff during the phone call.
- 26-week and 52-week exam/treatment appointments will be scheduled once the housing sites, IRB and CWRU have approved study personnel returning to being on-site at the housing sites

Once the COVID-19 pandemic ends, we will follow the original proposed plan.

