### 7.4 Withdrawal Visit

The following procedures will be followed for participants who choose to withdraw early or whose participation is terminated by the PI:

- Personal contact (by phone or in-person) by study staff will be made to confirm withdrawal.
- Record any adverse event reported by participant.
- Debrief about the interventions.
- Obtain responses to the study questionnaires (if applicable)
- If a participant withdraws or moves from the housing facility, visits and data collection will end with these participants being considered lost to follow-up. Data collected up to the point of withdrawal will be used for analysis.

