### 11.2 Sample Size Considerations (RC-3)

For continuous outcomes we computed power using a variance correction (i.e., variance inflation factor) to take into account possible correlations of outcomes within cluster. All computations of required effective samples sizes (or corresponding power) were done using the PASS 2005 software. For binary outcomes, we used a specialized program for cluster randomization (a non-inferiority test comparing two proportions).

The primary outcome tooth pain was defined as change in pain (based on a 100-mm visual analogue pain scale (VAS), where higher is worse pain) from baseline to 1 year. We assume a mean difference of 0 between SDF and ART+FV, and consider non-inferiority to be within a margin (mean difference) of 8 between SDF and ART+FV arms; and based on prior literature also assume a common standard deviation of 25. Further, we assumed an average of 25 subjects recruited per site, an intraclass correlation (ICC) of 0.01 (based on prior studies and literature), and a 15% dropout rate (based on prior studies). The use of a 0.025 alpha-level one-sided t-test to test the null hypothesis of inferiority versus the alternative hypothesis of non-inferiority (as defined above), 11 sites per treatment group (corresponding to 275 subjects per treatment group or 550 total) will provide an estimated 89% power to conclude non-inferiority. Even if the ICC is higher (0.02), there will still be 83% power to detect non-inferiority.

A second primary outcome is arrest rate. Previous data show a high arrest rate (of around 90%) for ART + FV. We expect a similar arrest rate for SDF. For the power calculation we suppose the unit of analysis to be the person, and consider the binary outcome of 'arrest' defined as all lesions for an individual being arrested. We assume equal (person-level) arrest rates of 90% for the ART+FV and SDF groups, and consider non-inferiority to be within a margin (difference in arrest proportions for ART+FV versus SDF) of 0.09. With the same assumptions as before using a 0.025 alpha level one-sided z test, the targeted sample size of 275 subjects in 11 sites per treatment group will provide an estimated 85% power to conclude non-inferiority. For a higher ICC of 0.02, there will still about 80% power to detect non-inferiority.

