Secondarily, we will extend the above GEE approach to analyze the repeated (baseline, 26 and 52-week) measures for each outcome. The models for each outcome will include the same prognostic variables as before, as well as time and a time by treatment interaction. We will allow for correlations among the repeated measures, e.g., using a first-order autocorrelation structure. If a substantial within-facility correlation is found we may need to incorporate facility as a second cluster levels (within which person – the first cluster level – is nested). We will estimate and test (via a robust t-test) the interaction term to compare trends over time for the two interventions. If the use of two cluster levels is not found to be feasible in the GEE approach, we will consider a generalized mixed effects model approach.

**Causal Inference standards (CI-1, CI-2, CI-3, CI-4):** Our use of randomization and adjustment in regression models should be sufficient to provide causally interpretable intervention effect estimates; special causal inference techniques such as propensity score or instrumental variable methods often indicated for observational studies, will therefore not be necessary for our data analysis. We will avoid biases in causal inferences about the intended interventions by using an intent-to-treat approach, in which individuals are analyzed according to randomized groups without regard to (extent of) treatment actually received.

**Sensitivity Analyses IR-5:** We will check sensitivity of conclusions to model assumptions as well as methodological decisions such as outcome definition. In particular, for the arrest outcome, our primary analysis is based on a binary indicator of 'complete' arrest of all lesions for an individual. We will seek to corroborate results from this approach with an alternative approach analyzing

number of lesions arrested. For the GEE analyses, planned for all outcomes, sensitivity will be assessed in part by using alternative working covariance structures and alternative sets of predictors. For some outcomes, alternative distributions will be considered; for example, for number of arrested lesions, possible distributions include Poisson, negative binomial, zero-inflated Poisson (ZIP), and zero-inflated negative binomial (ZINB). Sensitivity to assumptions regarding missing data will also be investigated as described further below.

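### Section 7.4 ends data collection for participants who move out, so obtainable 12-month pain and quality-of-life data are lost

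*Combined protocol and SAP*

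**What the plan says.** The stop rule is in section 7.4 of the protocol: "If a participant withdraws or moves from the housing facility, visits and data collection will end with these participants being considered lost to follow-up". Data recorded up to that point are kept for analysis. The opening of section 7.4 covers people who choose to withdraw or whose participation the PI ends. Section 5.5.1, which lists the reasons for withdrawal, does not name a change of address.

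Two places ask for a questionnaire on exit. Section 7.4 has "Obtain responses to the study questionnaires (if applicable" (its bracket closes there), and section 5.5.2 has "Complete the appropriate questionnaire nearest the drop out time point". Section 5.5.2 applies this to people who tell staff that they are dropping out.

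The means of reaching a mover are elsewhere in the protocol:

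- Section 7, under the temporary COVID-19 procedures: "Study staff will contact individuals due for the 26 and 52-week follow-up survey, to arrange a time to complete the survey by phone". A paper copy is mailed first. The same section adds: "Once the COVID-19 pandemic ends, we will follow the original proposed plan". In that plan (sections 7.2 and 7.3) the pain and quality-of-life surveys are interviews at the facility, and only the safety survey is routinely done by phone.
- Section 5.3: "Alternate contact information for family/friends that may be able to reach the participant if primary contact information becomes invalid will be obtained at recruitment".

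Section 11.2 defines the pain outcome as change from baseline to one year. The missing-data paragraph of section 11.4 says that the primary analyses use GEE on available observations under a missing-completely-at-random (MCAR) assumption. It also plans a check of that assumption and multiple imputation. No section exempts movers from the stop rule.

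**The concern.** A person who withdraws consent cannot be followed. A person who moves and still consents usually can be, at least by phone. Section 7.4 merges the two, so a consenting mover becomes lost to follow-up by rule, not through refusal or failure to be found.

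Tooth pain is a primary outcome and oral-health quality of life a secondary one. Neither needs an examination. An exit questionnaire does not replace the 52-week value, because the endpoint is defined at one year.

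People who leave independent senior housing may differ in health from those who stay. The documents give no data on this, but it is reason enough not to take MCAR for granted in this group. In a non-inferiority comparison, an outcome that can be observed should not be left to a missing-data model.

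**Working it through.** **Inputs (section 11.2).** 275 participants and 11 sites per arm, 25 per site, true difference 0, margin 8 on a 100-mm scale, SD 25, one-sided alpha 0.025, ICC 0.01 (alternative 0.02), and "a 15% dropout rate (based on prior studies" (its bracket closes there). The 15% is not split by cause, so the share of movers is unknown.

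**Formulas.** With loss d and ICC ρ:

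- effective n per arm = 275(1 − d) / [1 + (25(1 − d) − 1)ρ]
- SE = 25 √(2 / effective n)
- power = Φ(8/SE − 1.96)

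**Step 1: reproduce the plan's power at d = 0.15.**

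- ρ = 0.01: 233.75 / 1.2025 = 194.4; SE = 2.536; power = Φ(3.155 − 1.96) = 88.4% (plan: 89%).
- ρ = 0.02: 233.75 / 1.405 = 166.4; SE = 2.741; power = Φ(2.919 − 1.96) = 83.1% (plan: 83%).

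Both agree with the plan to within a percentage point.

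**Step 2: power if phone follow-up recovers movers.** Assume that movers lie inside the planned 15% loss and that all of them answer the 12-month survey by phone.

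| Movers (assumed) | Loss on pain | Pain outcomes kept, of 550 | Power, ICC 0.01 | Power, ICC 0.02 |
|---|---|---|---|---|
| none | 15% | 0 | 88.4% | 83.1% |
| 2% | 13% | 11 | 89.0% | 83.7% |
| 5% | 10% | about 28 | 89.8% | 84.5% |
| 10% | 5% | 55 | 91.0% | 85.8% |

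For example, at 10% loss and ICC 0.01: 247.5 / 1.215 = 203.7; SE = 2.477; power = Φ(3.230 − 1.96) = 89.8%. If only half of the movers are reached, the 2% to 10% range gives 88.7% to 89.8% (ICC 0.01) or 83.4% to 84.5% (ICC 0.02).

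**Step 3: how far missing outcomes could move the conclusion.** Take an observed difference of 0, equal loss in both arms and a fixed SE. An arm difference D among a missing fraction f then shifts the estimate by f × D.

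- The upper 95% limit at 15% loss is 1.96 × 2.536 = 4.97, which leaves 8 − 4.97 = 3.03 to the margin.
- If all 15% missing differ by arm: D = 3.03 / 0.15 = about 20 mm. At ICC 0.02 it is (8 − 5.37) / 0.15 = 17.5 mm.
- If only movers differ and they are 5%: D = 3.03 / 0.05 = about 61 mm. At ICC 0.02 it is 2.63 / 0.05 = about 53 mm.

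Movers alone, at 5%, would therefore need an implausibly large arm difference to reverse a result centred on zero. An observed difference nearer the margin would leave less room.

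**The case against.** Several points on the other side are sound.

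- **Intent-to-treat.** A reader might infer that the rule removes randomised participants from the intent-to-treat comparison. The documents do not support that. Section 11.4 defines the approach as one in which "individuals are analyzed according to randomized groups without regard to (extent of) treatment actually received". Stopping follow-up does not breach that definition. Earlier data are kept, the repeated-measures model can use them, and missing outcomes may be imputed.
- **Multiple imputation.** The plan does not rest on MCAR alone. It compares missing rates by arm, tests MCAR, imputes, and varies the imputation model. This stands, but for a mover the imputation can condition only on that person's data from before collection stopped, plus any exit questionnaire.
- **The phone procedure is temporary.** This stands. Using it for movers would be a new standing rule, not the use of one already in force for them.
- **Size and bias.** The mover rate is unknown, and the 15% allowance already covers loss of this kind. Poorer health among movers in both arms biases the difference only if the mover rate or the movers' outcomes differ by arm, and the documents give no reason to expect that. A reader might also infer that some definite share of the missing data would be recovered. Any such share only restates an assumption.
- **Partial remedy.** Caries arrest, the other primary outcome, needs an examination, and section 7.3 places it at the participant's own facility.

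These points limit the consequence. They do not show a reason to stop surveying a consenting participant because of a change of address.

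**Conclusion.** The point holds as a cheap improvement. Followed as written, section 7.4 discards 12-month pain and quality-of-life data that could be obtained from consenting movers. The effect on power is small: about 1.4 points if loss on pain falls from 15% to 10%, and about 0.6 to 2.6 points over an assumed 2% to 10% of movers, all reached, at ICC 0.01. The main gain is that fewer primary-outcome values depend on MCAR or on an imputation model.

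The documents do not show that the present rule biases the comparison, and the step 3 figures suggest that a small group of movers would seldom change the conclusion alone. The result rests on three assumptions: movers are part of the planned 15%, they can be reached by phone, and the section 11.2 inputs apply.

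**What to change.** In section 7.4, separate moving from withdrawal of consent:

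- For a mover who still consents, collect Questionnaire B (tooth pain/sensitivity and quality of life) by phone at the 26- and 52-week time points. Keep the section 7 phone procedure as a standing rule for this group after the COVID-19 measures end.
- Analyse movers under their original facility and arm.
- Stop data collection only when consent is withdrawn.
- Offer the 52-week examination where feasible.
- Report the number of movers by arm and time point, separately from withdrawals. The reasons that section 5.5.2 requires to be documented should allow this even for participants who have already left.

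This concerns data collection only, not treatment. The cost is a wording change and some extra calls, provided that the consent form (not among the pages available) permits contact after a move. Caries arrest stays missing for movers who cannot be examined. The history for version 14.0 (April 2023) refers to sites where recruitment was completed, so the new collection rule can help only participants still in follow-up.

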### 7.5 Unscheduled Visit

Unscheduled visits for participants may occur if an enrolled individual could not complete a scheduled study procedure during the timeframe study staff is scheduled to be on-site at the housing facility. In these cases, every attempt will be made by study staff to complete the dental screening/exam/treatment and/or data collection interview as near to the visit window as possible. Study data would be collected per protocol guidelines, but the time length between visits will be accounted for in the analysis stage if necessary.

## 8 STUDY PROCEDURES /EVALUATIONS

### 8.1 Study Procedures/Evaluations (IR-4)

Study procedures include interventions and survey/questionnaire performed to assess the primary outcome, secondary outcomes, and moderators. The intervention is based on study arm. Study Participants in Arm 1 receive silver diamine fluoride (SDF) while Arm 2 participants receive atraumatic restorative treatment (ART) and fluoride varnish (FV). There will also be a process evaluations (Safety, Satisfaction) at each of the interventions applied. See Table 8.1.1 for more details on the measure, sources, and timeline. The study timeline is as follows: Baseline visit ( $T_0$ ) (visual / tactile dental screening exam / 1st intervention), 26-week visit ( $T_{26}$ ) (visual / tactile dental screening exam / 2nd intervention), and 52-week visit ( $T_{52}$ ) (visual/tactile dental screening exam).

**Table 8.1.1 Quantitative Summary of measures, sources, and timeline (IR-4)**

Variable Type	Measure	Scale	Source	Timeline
Intervention by Study Arms	

• Biannual SDF (Arm 1)

• ART + biannual FV(Arm 2)

			$T_0, T_{26}$
Primary Outcome	Clinical dental exam 

• % freq of arrested surface/teeth

• Caries arrest

• overall score

		

• ICDAS Coronal and Root [Dikmen 2015]

	$T_0, T_{26}, T_{52}$

	Self-reported evaluation 
 
• Tooth pain/sensitivity
 
	
 
• overall score
 
	
 
• PROMIS v.1.0 - Pain Intensity 3a [Modified for Dental]
 
• Dental Discomfort Questionnaire [Modified for Adults from Versloot et al. 2006]
 
	T 0 , T 26 , T 52
Secondary Outcomes	Clinical dental exam 
 
• New decay
 
 Self-reported evaluation 
 
• OH-quality of life
 
	
 
• # freq of new decay teeth
 
• GOHRQoL overall score
 
	
 
• ICDAS Coronal and Root [Dikmen 2015]
 
• Geriatric Oral Health Quality of Life (GOHRQoL) [Atchison and Dolan, 1990]
 
	T 0 , T 26 , T 52 T 0 , T 26 , T 52
Process Outcome	
 
• Safety
 
• Satisfaction
 
	
 
• % freq. adverse event
 
• overall score
 
• overall score
 
	
 
• Safety Questionnaire (Pre- and Post-Exam/Treatment [Adapted for Adults from Milgrom et al. 2018]
 
• Treatment Satisfaction Questionnaire for Medication (TSQM) [Modified for Dental]
 
• Satisfaction with New Treatment for cavities [Modified for Adults from Crystal et al. 2017]
 
	T 0 , T 26 , T 52 T 52 T 52
Moderators	
 
• Socio-demographic
 
	
 
• % freq.
 
	
 
• NHANES III [CDC, 1988]
 
	T 0

	
 
• Medical Condition
 
• Oral Health Behavior
 
• Oral Health Symptoms
 
	
 
• % freq.
 
• overall score
 
• overall score
 
	
 
• Common Chronic Health Condition for Adults 65+ [Adapted from NCOA 2017]
 
• Oral Hygiene [Adapted from Kuusela 1997, WHO survey 1997]
 
• Self-Reported Measures of Current Oral Disease/Tissue Damage [Adapted from Gilbert et. al 1997]
 
	T 0
				T 0
				T 0

Pre-T0 = Prior to baseline

T0 = 0-week / Baseline visit / Baseline visual / tactile dental exam (Arm 1: SDF, Arm 2: ART + FV)

T26 = 26-week follow-up visit / Visual / tactile dental exam (Arm 1, Arm 2)

T52 = 52-week final visit / Visual / tactile dental exam (Final)

